Patients for the feasibility study will be recruited from the gastroenterology outpatient clinic at Bispebjerg Hospital, Copenhagen. Patients will be identified and invited by nurses and physicians at the outpatient clinic, who will describe the project and provide patients with written information about the project. If identified patients are willing and eligible to participate according to in – and exclusion criteria, the outpatient clinic staff will pass on the patients' contact details to intervention leader, TT, or a project nurse, employed at the gastroenterology department. Either TT or the project nurse will then contact the patients by telephone and invite them and a relative (if wished for) to an information meeting at the gastroenterology department. Here, the patients will receive oral information on the project by TT in a private room. This information will include the purpose, methods, time frame and possible risks of participating with sufficient time for the patients to understand and ask questions. Furthermore, the patients will be informed about the possibility of declining any new information on their health status that may emerge during the study, and additionally, the possibility to withdraw their consent at any time without it affecting their current treatment in the clinic. If patients decide to participate in the study during the information meeting, they will sign a written consent. However, patients will also be offered 48 hours

to reflect and decide on participation or not. Either TT or the project nurse will then obtain their signed consent at a later stage in the clinic.

Randomization and blinding

Study participants will be randomly assigned (1:1) to either an intervention group (n=15) or a control group (n=15). The randomization will be conducted through the REDCap (Research Electronic Data Capture) platform (see description under 'data management'). The allocation sequence will be concealed from the project leaders. It will not be possible to blind participants and project staff delivering the intervention to allocation status, whereas all outcome data will be collected by blinded outcome assessors.

Intervention

The intervention is an individually tailored, behavioural intervention addressing the individual patient's knowledge, motivation, resources and opportunities for increasing daily physical activity in the individual's everyday life.

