The SENS motion[®] (SENS Innovation ApS) is a waterproof activity sensor (45 × 23 × 5mm, 6 g), which the participants will wear laterally on the right thigh (20). The sensor is placed in a small patch specially designed for the SENS sensor and is attached on the skin with adhesive tape. The sensor is a triaxial accelerometer, which samples at 12 Hz and registers the orientation and acceleration of the thigh. Based on this orientation and acceleration, the sensor captures seven-day, 24-hour physical activity patterns, including number of steps and the amount of daily time lying down, sitting, standing, and being active with light, moderate and high intensity, as well as specific activities such as bicycling or walking stairs (28). SENS is used primarily as a single sensor system, but a dual-sensor algorithm has been developed to enable distinction between different sedentary positions, including sitting with inclined and upright backrest. Therefore, for the present study, we expect that two sensors will be used (one placed on the thigh and one on upper back). Patients will simultaneously be asked to fill in a diary reporting what time they get up in the morning, go to work, finish work and go to sleep for the seven-day measurement period.

Self-reported physical activity and sitting time

Self-reported physical activity (light, moderate, vigorous) and sitting time at work and during leisure time will be measured by the Physical Activity Scale 2.1 (PAS 2.1) (21), a modified version of the original PAS

questionnaire, which has previously been validated against accelerometer, physical activity logs and maximum oxygen uptake (22,23). Respondents will be asked to specify number of hours and minutes in an average 24-hour day spent sitting at work and during leisure time. In addition, participants will report number of weekly hours and minutes spent in light, moderate or vigorous intensity activities.

The participants will be asked to respond to PAS 2.1 at baseline and again at the 20-week follow-up assessment. In addition, the project nurses will conduct a telephone-based mini-survey four times with each participant during the intervention period in order to monitor changes in physical activity behaviour in-between the two outcome assessment times. The survey will consist of three questions about the participant's weekly time spent on moderate to vigorous physical activity, light-intensity physical activity and sedentary behaviours.

Exercise self-efficacy

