Outcome assessment will be conducted at study inclusion/baseline and repeated at end of the intervention period (20 weeks (five months) from baseline) for each of the 30 participants. Participants will complete self-administered questionnaires regarding demographics, lifestyle, physical activity, disease-specific quality of life, pain, fatigue and intrusiveness of IBD. Anthropometric measures, blood pressure, fecal calprotectin test and a single blood sample will be obtained at the same time points by a project nurse. Calprotectin test and blood samples will be analyzed at Department of Clinical Biochemistry, Bispebjerg Hospital, for inflammation biomarkers and lipid status. In addition, the same project nurse will attach the SENS motion activity sensor on the participants' thigh and instruct participants how to wear the monitors 24 hours per day for seven continuous days. The activity sensors connect wirelessly to a smartphone application, and the recorded data are transmitted to the application every 10 minutes, when the smartphone is within network reach or stored on the sensor for later transmission. The raw triaxial accelerometer data are transferred automatically to a secure web server (Capital Region, Denmark) via the smartphone. During each assessment the participants will fill in a daily report of their resting and sleeping time in order to isolate their sitting time from sleeping time. After the seven-day assessment period the participants will remove the sensor and keep it until the next appointment at Bispebjerg Hospital, where they will return it to the project nurse.

Data collection from feasibility and acceptability

Regarding data on feasibility and acceptability, the intervention leader (TT) will document all components of the recruitment and screening procedure. This will include documentation of the number of invited and screened patients and reasons for exclusion or declining study participation. Acceptability and fidelity to the intervention elements and outcome assessments will be evaluated through interviews with project staff delivering the intervention and with five study participants. Furthermore, this will be monitored using a log sheet in which information on intervention progress and retention will be registered.

Data management

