Descriptive statistics in the feasibility study will give insight into participants' characteristics as well as distributions and indications of change in the outcome measures. The descriptive statistics will summarize categorical data (frequencies (%)) and continuous data (medians, means (M) and standard deviations (SD)). Changes in outcome measures from baseline to end of intervention will be reported as within-group differences (M and SD) in the intervention and the control group separately and between-group differences in change will be summarized (M, SD). All analyses will be conducted using SAS software (v. 9.3; SAS Institute Inc., Cary, NC, USA).

Risks and adverse events

The SENS motion activity sensor is sealed and placed in a small patch to avoid direct contact with the skin. The participants will be encouraged to change the location of the unit or contact intervention leader (TT) if the patch comes off or if they experience skin redness or itching. In our previous studies using activity monitors on patients with rheumatoid arthritis, few cases of redness and itching were reported as the only adverse events from using the monitors along with the inconvenience of having the unit attached to thigh and/or shoulder (17). Adverse effects such as muscle soreness, joint pain, muscle cramps and increased need to rest may be expected as participants are encouraged to be more physically active. Routine stool and blood samples are included in the study. The blood samples are taken by experienced staff and carried out in a quiet shielded room. A foreseeable risk involves the possible discomfort and small hematoma following the sampling of blood from the antecubital vein.

Ethical considerations

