The study will be conducted according to the Danish Health law and the General Data Protection Law (GDPR) regarding handling of personal data. Approval by the Regional Scientific Ethical Committee of the Capital Region of Denmark will be obtained before initiation of the study. Both oral and written informed consent will be obtained before entering the study in compliance with the Declaration of Helsinki. In a patient perspective, the benefits of participating in development and testing of a physical activity intervention on health outcomes is believed to outweigh the disadvantages. The physical tests and self-reported measurements comprise no foreseeable risks for the participants. In fact, the blood sample and fecal calprotectin tests are part of routine testing in the gastroenterology outpatient clinic. As the potential scientific benefits of conducting these studies outweigh the discomfort, which some participants may experience, we believe that the ethical aspects of the studies are feasible and that the overall research results may lead to individually targeted, improved health in patients with IBD and strengthened capacities in healthcare professionals.

Time Schedule

The overall project started up March 1st 2022, where the epidemiological part was initiated. The intervention part will be initiated Aug 1st 2022 and the development of the intervention was conducted in ultimo 2022/primo 2023. We expect the feasibility study (study IV) to start in October/November 2023.

	2022 Project start: March 1 st				2023				2024 Project end: Dec 31 st			
PART I : Epidemiological studies. March 1st 2022												
Preparation and Data management.												
Statistical analyses.												
Preparation of scientific manuscripts												
Results for interventions studies												
PART II: Intervention studies. Aug 1st 2022												
Observation, stakeholder consultations												
Co-creation, workshops, intervention development												
Conduct of feasibility study												
Preparation of scientific manuscripts												

Perspectives

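### Adverse effects of being more active are expected, but no adverse-event collection over the 20 weeks and no event count by arm is specified, so tolerability can be judged only incompletely

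*Combined protocol and SAP*

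**What the plan says.** **Expected effects.** 'Risks and adverse events' says that "Adverse effects such as muscle soreness, joint pain, muscle cramps and increased need to rest may be expected" because participants are encouraged to move more. No method of collecting, recording or reporting follows. The only instruction tied to a harm concerns the sensor: participants are to move it or "contact intervention leader (TT) if the patch comes off or if they experience skin redness or itching".

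**Contact between assessments.** Under 'Self-reported physical activity and sitting time', "the project nurses will conduct a telephone-based mini-survey four times with each participant during the intervention period". The content is fixed: "The survey will consist of three questions about the participant's weekly time spent on moderate to vigorous physical activity, light-intensity physical activity and sedentary behaviours".

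**Assessments.** Outcome assessment takes place at baseline and is "repeated at end of the intervention period (20 weeks (five months) from baseline) for each of the 30 participants". The instruments include a pain VAS with pain site, the MFI-20 for fatigue, the IBDQ-32, fecal calprotectin and CRP. 'Control group' says that controls have the same baseline and outcome assessments.

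**Process data.** 'Data collection from feasibility and acceptability' provides for interviews with project staff and five participants on acceptability and fidelity, and a log sheet on intervention progress and retention.

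**Analysis.** '(Statistical) analyses' covers screening and eligibility numbers, retention, adherence and data completeness. Changes in the outcome measures are summarised for each arm and between arms. Adverse events are not mentioned.

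**The concern.** The study is meant to show whether the intervention model is applicable to these patients before a large RCT. Tolerability is part of that question. The Background describes a disease with flares and fluctuating activity, in which fatigue, abdominal pain and physical weakness are dominant barriers to exercise. Several effects expected from the intervention resemble those background symptoms. A randomised control arm can help to separate the two, but only if both arms are asked the same question.

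As planned, a musculoskeletal complaint or a flare in, say, week 8 reaches the data only if the participant volunteers it and someone chooses to write it down. The report could then truthfully state that no adverse events were recorded, and a reader could not tell absence of events from absence of questions. Unlike a missing table, this cannot be repaired at analysis, because the data would not exist.

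**Working it through.** The documents give no adverse-event rate, no derivation of the sample size and no harms figure, so there is nothing to reproduce. The check has two parts.

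**1. What is measured for each expected effect**

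| Effect named in the plan | Measure in both arms, baseline and week 20 | Recorded as an event? |
|---|---|---|
| Joint pain | Indirect: pain VAS and pain site | No |
| Increased need to rest | Indirect: MFI-20 | No |
| Muscle soreness | Only what the pain item happens to catch | No |
| Muscle cramps | None | No |

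IBDQ-32, calprotectin and CRP reflect disease activity at the same two times. These measures leave three gaps. Two measurements 20 weeks apart miss an event that begins and resolves between them. A mean change by arm does not show how many participants were affected. Nothing records whether a change was an injury, a flare or an effect of the activity.

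**2. What a count by arm could show with this sample**

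Inputs: n = 15 per arm ('Randomization and blinding') and 5 interviewed participants ('Data collection from feasibility and acceptability'). The true event rate p is an assumption, varied from 5% to 30%. Every participant is taken to answer.

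Chance of at least one affected participant = 1 − (1 − p)^n.

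| Assumed p | One arm, n = 15 | Five interviewees, n = 5 |
|---|---|---|
| 5% | 53.7% | 22.6% |
| 10% | 79.4% | 41.0% |
| 20% | 96.5% | 67.2% |
| 30% | 99.5% | 83.2% |

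The last column is favourable to the interviews: it assumes that all five interviewees come from the intervention arm and that each would mention an event.

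Precision, by exact (Clopper-Pearson) two-sided 95% limits:
- 0 of 15: upper limit = 1 − 0.025^(1/15) = 0.218, that is 21.8%.
- 5 of 15 (33.3%): 11.8% to 61.6%.

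An arm-level count would probably show an effect that is common, but it could not estimate a rate closely or support a comparison of arms beyond description.

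**The case against.** The strongest reply is that the plan is not silent on these effects. Pain with its site, fatigue, bowel and systemic symptoms and inflammation markers are all measured in both arms, and their changes are reported by arm. Retention, receipt of each intervention element and the interviews also bear on tolerability. All of this stands, and it rules out two stronger readings:

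- A reader might infer that the plan never asks about the expected effects. It does so in part for joint pain and need to rest, and incidentally for muscle soreness. What is missing is their collection as events, and any item for cramps.
- A reader might infer that tolerability cannot be judged at all. Indirect evidence exists, but it is incomplete.

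A third reading is also tempting: that 'Ethical considerations' contradicts the risk section by saying "The physical tests and self-reported measurements comprise no foreseeable risks for the participants". That sentence is about tests and self-reports, not about the intervention, so it does not conflict with the effects expected from being more active.

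One might also expect spontaneous reports to come mainly from the intervention arm, because it alone has four counselling sessions. The documents do not settle this. The mini-survey is described as going to each participant, which would give controls four nurse contacts too. 'Control group', however, commits controls only to the baseline and outcome assessments.

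Finally, any fix by telephone has a weakness. The calls are made by project nurses, a project nurse delivers the counselling, and 'Randomization and blinding' accepts that staff delivering the intervention are not blinded. Identical wording does not guarantee identical questioning. This limits what the calls can show and shapes the fix; it does not remove the gap.

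**Conclusion.** The point holds in limited form. The plan expects four kinds of adverse effect, yet specifies no adverse-event collection during the 20 weeks and no count of affected participants by arm. The scores at two time points, together with retention, adherence and interviews, are only indirect evidence, so the RCT would be designed on an incomplete picture of tolerability.

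The textual finding needs no numerical assumption. The sample-size figures rest on 15 responders per arm, and the detection chances also on assumed event rates, since the documents give none. Any count will be imprecise, because 0/15 still allows a true rate of up to about 22%. It should be presented as description, not as a test of safety. The change is worth making before recruitment, because uncollected events cannot be recovered later.

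**What to change.** 1. Add one identically worded question to the self-administered week-20 questionnaire in both arms: any new or worse symptoms, injury, IBD flare or change in IBD medication since the start of the study.
2. Add the same question, with the period since the last contact, to each mini-survey call. State under 'Self-reported physical activity and sitting time' that control participants also receive the mini-survey, and align 'Control group' with this.
3. Record the answers in the eCRF.
4. Under '(Statistical) analyses', report by arm the number and percentage of participants with at least one event, descriptively. Show the two sources separately.

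The week-20 item is the cleaner comparison between arms, because no unblinded caller puts the question. It relies on longer recall, and participants know their allocation. The calls are better placed to catch transient events.

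**Cost.** One question, one eCRF field, one table and about a minute per call. If controls are not called at present, this adds up to 15 × 4 = 60 short calls. The intervention and the sample size do not change.
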